Brief Sleep Hygiene Education: During stabilization, staff will conduct a brief educational session with participants to provide information regarding appropriate sleep hygiene (Doshi et al., 2017). This session will ensure all participants have the same understanding of healthy sleep behaviors before the taper begins, to minimize the impact that differences in sleep hygiene has, and better isolate the impact of SUVO on study outcomes.

Overdose Education: During the stabilization period, participants will also complete a brief opioid overdose prevention computerized education session (developed by Co-I Dunn under NIDA R21DA035327).

Randomization to Group: Participants will be stratified into experimental group based on (a) baseline Pittsburgh Sleep Quality Index (PSQI) (<5/≥5), (b) peak SOWS ratings during buprenorphine induction (≤10/>10), (c) buprenorphine stabilization dose (<16mg/16mg), and (d) sex (M/F). Randomization will occur via a minimization procedure to balance the distribution of these characteristics

across the experimental groups. Study pharmacist staff, who have no direct participant contact, will oversee randomization and dispensing of study medications.

Taper Phase (4 days): Participants will undergo an open-label, step-wise buprenorphine taper. An open-label phase is necessary because buprenorphine placebo tablets/filmstrips are not available; however, this open-label design feature is of value because it increases the overall generalizability of the study results.

Post-taper Phase (4 days): Participants will continue study participation for four days (three nights) following buprenorphine discontinuation, to capture the full course of opioid withdrawal.

Study Medications: Double-blind study medication dosing will begin on the evening before Taper Day 1. Study medications will either be 20mg SUVO, 40MG SUVO, or placebo, which will be administered prior to bedtime. Though participants will be reminded to practice good sleep hygiene, no contingencies or consequences will be associated with their sleep behavior. This is because our extensive experience suggests that participants who are unable to sleep at night will attempt to sleep during the day; all sleep attempts will be captured by wrist actigraphy and nightly questionnaires and evaluated as outcome data. Placing contingencies on sleep parameters (such as no day-time sleeping) could also prompt attrition.

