The first primary outcome for this study will be total sleep time during opioid withdrawal as determined by EEG, and supplemented by actigraphy and self-report.

The second primary outcome for this study is abuse liability, which will be assessed via next day measures of Drug Liking measured on a 0-100 point VAS.

b. Secondary outcome variables.

(1) Secondary outcomes from the Sleep Profiler EEG will include measures of sleep continuity and architecture

(2) Secondary actigraphy outcomes will include sleep and activity-related outcomes

(3) Secondary self-report sleep ratings will include self-reported sleep measures

(4) Opioid withdrawal severity, assessed via the subjective opiate withdrawal scale.

(5) Other secondary outcomes include a hypothetical purchasing task, other self-report VAS measures of abuse liability (e.g. drug effect, good effect, bad effect, perceived drug value), self-reported measures of drug craving, VAS opioid withdrawal, stress; diurnal cortisol; vital signs; and retention in treatment.

c. Statistical plan including sample size justification and interim data analysis.

Power Analyses: In order to support the planned 2 and 3 group analyses (comparing 20mg SUVO, 40mg SUVO, and placebo), we used G-power to derive sample sizes from previously reported effect sizes in clinical trials on SUVO and hypothetical opioid purchase task data; both displayed large effect sizes (≥ 0.70). A total sample size of 36 participants (12 per group) would provide 95% power to detect an effect size of 0.70 for difference in total sleep time (Primary Aim 1) and difference in the opioid demand curve (Secondary Aim 1). A study on the abuse liability of SUVO, zolpidem, and placebo in non-ODU patients (Schoedel et al., 2016) reported a medium to large effect size on drug liking (0.45), suggesting a total sample size of 34 would provide 90% power to detect an effect size of 0.45 for Primary Aim 2. To protect against participant drop out, we are proposing to enroll 15 participants per medication group (total N=45).

Analyses: All Primary Outcomes (total sleep time, opioid withdrawal severity, and abuse liability) will be compared as a function of group (20mg SUVO, 40mg SUVO, and placebo; or SUVO [collapsed] vs placebo) and phase (taper vs. post-taper), as well as group by day (7 nights) using 2-factor Proc Mixed analyses with Tukey posthoc testing. Both peak values and Area-under-the-curve (AUC) values of total sleep time, SOWS scores, and Drug Liking

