will be derived for (a) the entire study, (b) the taper period, and (c) the post-taper period. These outcomes will be compared as a function of group and group x phase using independent groups t-tests and ANOVAs with Tukey post-hoc for pairwise comparisons. If data does not meet ANOVA assumptions, mixed model regressions will be used.

Secondary outcomes from the Sleep Profiler EEG may include measures of sleep continuity (sleep latency, sleep efficiency [total sleep time/time spent in bed], wake after onset [WASO], number of awakenings) and architecture (time spent in stage 1, stage 2, stage 3, and rapid eye movement [REM] sleep). (b) Secondary actigraphy outcomes may include wake after sleep onset (WASO), time spent napping, number of naps, and total activity. (c) Secondary self-report ratings may include subjective WASO, VAS sleepiness and quality of sleep, and Stanford Sleepiness Scale score. **Analyses:** All outcomes will be compared as a function of group (20mgSUVO, 40mg SUVO, and placebo) and phase (taper vs. post-taper), as well as group by day (7 nights) using 2-factor Proc Mixed analyses with Tukey posthoc testing. Area-under-the-curve (AUC) values for the entire study and the taper and post-taper periods will then be derived and compared as a function of group and group x phase using independent groups t-tests and ANOVAs with Tukey post-hoc for pairwise comparisons. If data does not meet ANOVA assumptions, mixed model regressions will be used.

Secondary actigraphy outcomes may include wake after sleep onset (WASO), time spent napping, number of naps, and total activity. Secondary self-report ratings may include subjective WASO, visual analogue scale (VAS) sleepiness and quality of sleep, and Stanford Sleepiness Scale score. All outcomes will be compared as a function of group (20mg SUVO, 40mg SUVO, and placebo) and phase (taper vs. post-taper), as well as group by day (7 nights) using area-under-the-curve (AUC). The taper and post-taper periods will then be derived and compared as a function of group and group x phase using independent groups t-tests and ANOVAs with Tukey post-hoc for pairwise comparisons. If data does not meet ANOVA assumptions, mixed model regressions will be used.

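### Peak total sleep time is the participant's longest, least disturbed night, so the whole-study peak is insensitive to rescue of bad nights and drifts modestly with retention

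*Combined protocol and SAP*

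**What the plan says.** Section 7.a sets the target: "The first primary outcome for this study will be total sleep time during opioid withdrawal as determined by EEG". Section 7.c (Analyses) first plans a mixed model by group and phase, "as well as group by day (7 nights) using 2-factor Proc Mixed analyses with Tukey posthoc testing". It then adds summary measures: "Both peak values and Area-under-the-curve (AUC) values of total sleep time, SOWS scores, and Drug Liking". On the time windows it states that these "will be derived for (a) the entire study, (b) the taper period, and (c) the post-taper period". On testing it says: "These outcomes will be compared as a function of group and group x phase using independent groups t-tests and ANOVAs". Pairwise contrasts use Tukey's method.

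One peak rule thus covers three outcomes. The plan does not define the word, give it a direction, or set a minimum number of nights. Nor does it say which of mixed model, peak or AUC decides the first primary outcome.

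The two phases differ in length. Section 4.a gives a four-day taper, then a post-taper phase of "four days (three nights) following buprenorphine discontinuation". With seven nights in the model, that leaves 7 − 3 = 4 for the taper.

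**The concern.** For SOWS the maximum is the most severe withdrawal, and for Drug Liking the strongest abuse signal. For total sleep time the maximum is the night on which the participant was least disturbed, which is the wrong end of the distribution for a trial of sleep loss in withdrawal. A drug that lifts short nights can leave the longest night almost unchanged.

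A maximum also grows with the number of values it is taken over. Participants may leave early (Sections 4.f and 7.d), and better retention on suvorexant is a hypothesis of Secondary Aim 1, so the arms may contribute different numbers of nights.

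The plan names no deciding summary. A null or slightly tilted peak result could therefore be reported as a primary-outcome finding and influence which dose goes into the subsequent study mentioned in the Abstract.

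**Working it through.** **Plan's own figure.** Section 7.c states 95% power for total sleep time with 36 participants and effect size 0.70. Read as Cohen's f in a three-group ANOVA at α = 0.05 (the documents state no α), the noncentrality is 0.70² × 36 = 17.64 and power is 95.7%. The figure reproduces. The plan does not say which summary of total sleep time it applies to.

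**Inputs.** From the documents: 7 nights, split 4 and 3; 12 per group for power; 15 per group enrolled. Assumed, because the documents give none: night-to-night and between-person SDs of 60 min (other values where shown), independent normal nights, two-sided α = 0.05, the effect patterns and the dropout shares.

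**Step 1: sensitivity.** The table gives simulated power for one active arm against placebo. Ranges span separate runs, and in the last row the assumed SDs too.

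| Drug effect (assumed) | Window | Peak | Mean | Lowest night |
|---|---|---|---|---|
| +60 min on each person's four worst nights | whole study | about 5% | 23-26% | about 48% |
| 90-min post-taper dip, 60 min restored | whole study | about 6% | about 15% | about 33% |
| Same | post-taper | 46-47% | 52-53% | about 47% |
| +60 min every night | whole study | 51-52% | 59-61% | about 50% |
| Fall from 400 to 310 min, halved by drug (15 per arm; between-person SD 50, within-person 45-90) | whole study | 8-9% | 16-24% | 17-39% |

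The mean column can be checked by hand. The SD of a person's seven-night mean is √(60² + 60²/7) = 64.1 min. The gain in the mean is 60 × 4/7 = 34.3 min in the first row (0.53 SD), 60 × 3/7 = 25.7 min in the second (0.40 SD), and 60 min under a uniform gain (0.94 SD).

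**Step 2: night count.** The expected maximum of k independent normal nights, above the person's own mean and in night-to-night SDs, is k∫xφ(x)Φ(x)^(k−1)dx:

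- 3 nights: 0.846
- 4 nights: 1.029
- 7 nights: 1.352

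*Phase.* The difference is 1.029 − 0.846 = 0.183 SD, or 11 min at an SD of 60 and 16.5 min at 90. Every arm has the same 4 and 3 nights, so this offset is common to all arms and drops out of the group and group-by-phase contrasts. Simulated null rejection for group by phase was 5.3%.

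*Retention.* If some participants leave after night 3 and the drug has no effect, the arm-level bias is (difference in share leaving) × (1.352 − 0.846) × SD. At an SD of 60:

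- 0% v 30%, or 10% v 40%: 0.30 × 0.506 × 60 = 9.1 min
- 20% v 40%: 0.20 × 0.506 × 60 = 6.1 min

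Simulation with 15 per arm gave 6-10 min and type I error of about 6%. Across SDs of 45 to 90 min the range was 4.5-14 min and 5.4-7.3%. Mean sleep time per observed night stayed unbiased, at about 5%. The lowest night was biased by 6-10 min in the opposite direction.

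**The case against.** The best defence is that the plan does not rest on the whole-study peak. The mixed model over seven nights comes first, and peak is also derived within each phase. Where the drug restores sleep only after the taper, the post-taper peak recovers nearly the full 60 min with 46-47% power, and the group-by-phase contrast on peak reaches 63%. Dosing is nightly, and a steady nightly gain shows in the peak almost as well as in the mean. The worst-four-nights pattern spares the maximum largely by construction, and nothing in the documents makes it the expected one. All of this stands, and it confines the sensitivity problem to the whole-study peak under uneven effects.

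The authors may also have meant peak disturbance. The text does not say so, and if that was the intent the wording still has to change.

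Three stronger readings are tempting and are not supported:

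- A reader might infer that the plan misses withdrawal insomnia. It does not, because the mixed model captures it.
- A reader might infer that 4 v 3 nights creates false phase findings. The offset cancels in the two comparisons named for peak and matters only if phase values of peak are compared directly.
- A reader might contrast seven nights with two and infer an arm difference of 47-71 min (SD 60-90). That is a gap between two individuals. At arm level the bias is about 6-10 min.

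**Conclusion.** The point holds in a limited form. Applying peak to total sleep time selects the least disturbed night. Over the whole study it has about 5% power for gains confined to bad or post-taper nights, where mean nightly sleep time has 15-26% and the lowest night 33-48%. It also carries a modest retention bias of about 6-10 min toward the better-retained arm, with type I error about 6%.

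That peak means the longest night follows from the ordinary meaning of the word. The sizes rest on assumed SDs, effect patterns, dropout shares and independent nights, none of which the documents supply. This is a poorly chosen supplementary summary of a primary outcome. It does not show that the primary aim cannot be answered.

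**What to change.** In Section 7.c, delete peak for total sleep time and keep it for SOWS and Drug Liking. Name mean nightly total sleep time per phase, estimated from the Proc Mixed model already planned, as the summary for the first primary outcome. If an extreme value is wanted, use the lowest night only over a fixed, equal number of post-randomisation nights, because otherwise it has the same night-count bias in reverse.

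This is a short text change using the same EEG data, and it should be made before unblinding. The downside is the loss of one supplementary summary.

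### Unscaled AUCs of total sleep time over 4 taper and 3 post-taper nights turn a constant nightly benefit into a group x phase interaction

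*Combined protocol and SAP*

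**What the plan says.** In section 7.c, Analyses, the primary outcomes are compared by group and phase, "as well as group by day (7 nights) using 2-factor Proc Mixed analyses with Tukey posthoc testing". The plan then adds two kinds of summary measure: "Both peak values and Area-under-the-curve (AUC) values of total sleep time, SOWS scores, and Drug Liking". It names three windows for them, which "will be derived for (a) the entire study, (b) the taper period, and (c) the post-taper period". On the comparison itself, the plan states: "These outcomes will be compared as a function of group and group x phase using independent groups t-tests and ANOVAs". No rule for computing the AUC is given: not sum or trapezoid, not the endpoints, and not whether it is divided by nights or duration.

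The night counts come from section 4.a. Under Post-taper Phase: "Participants will continue study participation for four days (three nights) following buprenorphine discontinuation". Under Study Medications: "Double-blind study medication dosing will begin on the evening before Taper Day 1".

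The secondary outcomes in 7.c follow the same pattern. The first secondary paragraph covers EEG, actigraphy and self-report sleep measures. It plans Proc Mixed and then says "Area-under-the-curve (AUC) values for the entire study and the taper and post-taper periods will then be derived and compared". The next paragraph lists the same actigraphy and self-report measures again, but with the comparison "as well as group by day (7 nights) using area-under-the-curve (AUC"), and mixed regression only as a fallback. The last paragraph of analyses uses that second wording for the purchase task, withdrawal, craving, stress and cortisol measures.

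**The concern.** An AUC in its ordinary form grows with the length of its window. When two windows differ in length, a treatment effect that is identical every night produces a larger AUC difference in the longer window. A group x phase test on those AUCs then partly tests the number of nights.

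A reader would take such an interaction to mean that suvorexant's effect on sleep changes once buprenorphine has stopped. That is a natural clinical question in this trial, and the answer should not depend on an unstated AUC convention. The result could also disagree with the Proc Mixed group x phase test of the same data, and the plan does not say which of the two governs.

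**Working it through.** **Inputs from the documents.** Taper phase 4 days; post-taper 4 days and 3 nights (4.a). Residential stay 11 days, 10 nights (4.a, Clinical Research Unit). Stabilization 3 days (6.a, Buprenorphine). Analysed nights 7, and 12 per group (7.c).

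**Night count, reproducing the plan's figure.** Days: 3 + 4 + 4 = 11. Nights: 10 - 3 stabilization nights = 7, as stated. With 3 post-taper nights, the taper has 7 - 3 = 4.

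**Interaction from a constant benefit d per night.** The spurious interaction is d times (sum of taper weights minus sum of post-taper weights):

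| AUC convention | Taper | Post-taper | Interaction |
|---|---|---|---|
| Plain sum | 4d | 3d | d |
| Trapezoid within each phase | 3d | 2d | d |
| Trapezoid, post-taper starting at the last taper night | 3d | 3d | 0 |
| Mean per night, or trapezoid divided by its width | d | d | 0 |

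**How often it would be significant.** The documents give no nightly SD, correlation or d, so these are assumptions: SD 60 min, equal correlation r between nights of 0.3 to 0.8, means 0/d/d in the three arms, 12 per group with full stay, two-sided 5%.

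*Within-person contrast (taper AUC minus post-taper AUC).* The variance is 60² x [(1 - r)S + r], where S is the sum of squared weights: 7 for the sum, 4 for the within-phase trapezoid. The noncentrality is 12 x d² x (2/3) / variance, with 2 and 33 df. Example at r = 0.5, d = 60:

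- Sum: variance 3,600 x (3.5 + 0.5) = 14,400; noncentrality 28,800 / 14,400 = 2.0; rejection 20.9%.
- Within-phase trapezoid: variance 3,600 x (2.0 + 0.5) = 9,000; noncentrality 28,800 / 9,000 = 3.2; rejection 31.4%.

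| d (min) | Sum, r = 0.3 to 0.8 | Within-phase trapezoid, r = 0.3 to 0.8 |
|---|---|---|
| 30 | 7.7-11.8% | 9.7-14.5% |
| 60 | 17.0-35.2% | 26.0-46.6% |
| 90 | 33.7-68.5% | 52.9-82.6% |

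The mean per night stays at 5%.

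*Phase as an independent factor in a two-way ANOVA* (simulation, 20,000 replicates): 0-1% at 30 min, 0-4% at 60, 0-15% at 90. The rates are low because the between-person variation stays in the error term. The estimate is still off by d.

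**First dosed night.** If dosing runs nightly to the end of the stay, the evening before Taper Day 1 plus 4 + 3 gives 8 dosed nights against 7 analysed. If that night were added to the taper in a plain sum, the interaction would be 5d - 3d = 2d.

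**The case against.** The strongest reply is that the plan is incomplete here and not demonstrably wrong. No sentence says that the AUC is unscaled, and one reasonable trapezoid gives no artefact. That is correct, and it is why the finding is conditional. But the two simplest conventions do produce the artefact, and nothing in 7.c steers the analyst away from them.

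Four stronger readings are tempting, and the documents do not support them.

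- *The primary sleep result is compromised.* It is not. No aim rests on group x phase. Proc Mixed on nightly values does not depend on phase length. Nor do group comparisons within one phase, or over the whole study, among participants with a full stay.
- *The secondary sleep outcomes have no unaffected test.* The second actigraphy and self-report list, read alone, suggests this. The paragraph before it already puts the same measures under Proc Mixed. The two need reconciling, but the test is there.
- *Every AUC outcome is affected.* Withdrawal and Drug Liking ratings, and most of the last paragraph's measures, are taken by day, and both phases last four days. They are affected only if the seven-night window is applied to them.
- *False interactions would be frequent.* The larger rates need a within-person contrast. The text names t-tests and ANOVAs for independent groups and no repeated-measures analysis. If phase is an independent factor, the rates stay at or below about 4% up to 60 min.

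A reader might also infer that a whole-study AUC would count longer retention as more sleep. For example, with no drug effect, 360 min per night, and 20% of placebo v 0% of suvorexant participants leaving an average of 2.5 nights early, a sum over attended nights differs by 0.20 x 2.5 x 360 = 180 min. Each of these figures is assumed. The plan does not say how a leaver's AUC is formed, an AUC in completers only would not show this, and Secondary Aim 1 asks whether retention improves without asserting that it will. This is a further reason for scaling, not a separate defect.

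**Conclusion.** The point holds as a minor one. With 4 and 3 analysed nights and no scaling, a plain sum or within-phase trapezoid of total sleep time misstates the group x phase interaction by exactly d when the nightly benefit is constant. That part is algebra and needs no assumption beyond the AUC convention. Its statistical consequence is uncertain, because it depends on the assumed SD, correlation and benefit and above all on which ANOVA is meant. The harm is confined to a supporting analysis of nightly sleep outcomes.

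**What to change.** In 7.c:

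1. For nightly sleep outcomes, replace the phase and whole-study AUCs with the mean per observed night, or divide the AUC by its duration. This also keeps length of stay out of the value if early leavers are included. For daily outcomes, use the mean per observed day or the same number of days in each phase. The within-day cortisol AUC is a different quantity and stays.
2. Where AUC and Proc Mixed address the same group x phase question, take the conclusion from Proc Mixed. Reconcile the two actigraphy and self-report lists, which name Proc Mixed in one paragraph and AUC in the next.
3. State whether the night of the first dose is among the seven analysed nights and, if so, to which phase it belongs.

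The cost is SAP wording and a small change to analysis code, with no new data. The downsides are that AUC units become per-night values, and that a short, noisier stay gets the same weight as a full one. A leaver's mean can also be slightly off if sleep trends over nights, and a leaver with no post-taper night has no post-taper mean; both are reasons to rest the phase conclusion on the mixed model.
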